14.1. Futility Analysis

Futility analysis (FA) will be performed when the Cycle 6 tumor assessment data are available for the first 15 evaluable subjects regardless of EZH2 status. ORR, defined as the proportion of the subjects achieving a CR or PR according to the 2014 Lugano Classification (Appendix 3), will be calculated. Subjects with the best response of unknown/non-evaluable response will be treated as non-responders, (i.e., they will be included in the denominator only when calculating ORR).

14.2. Primary Efficacy Analyses

ORR is defined as the proportion of subjects achieving a CR or PR according to the 2014 Lugano Classification (Appendix 3) as assessed by Investigator and blinded IRC at the following time points: Cycle 3, Cycle 6, Cycle 12, Cycle 18, and Cycle 24.

Subjects with a best response of unknown/non-evaluable response will be treated as non-responders, (i.e., they will be included in the denominator only when calculating the percentage). ORR will be presented with corresponding 2-sided 95% confidence intervals (CIs). This analysis will be performed on a subset of the FAS that includes all subjects with WT EZH2 status.

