Safety will be assessed through summaries of AEs, laboratory evaluations, vital signs, and physical examinations. Safety analyses will be based on all enrolled subjects who receive at least 1 dose or partial dose of study drugs (safety population). Drug exposure will be summarized by descriptive statistics. Severity of all AEs is to be evaluated by the Investigator based on the CTCAE, version 5.0 and will be coded to preferred term, higher level term, and system organ class using the Medical Dictionary for Regulatory Activities (MedDRA; version 23.1). The number and percentage of subjects with AEs will be presented by MedDRA system organ class and preferred term, relationship to study treatment, and severity. Descriptive statistics will be used rather than inferential statistics. Laboratory values also will be classified by toxicity grade based on the NCI's CTCAE, version 5.0. Laboratory shift tables of the baseline results to each of the subsequent visits will be produced.

Statistical Methods:

Primary Efficacy Endpoint - All Phase 2 Cohorts

• ORR: ORR is defined as the proportion of the FAS subjects with WT EZH2 status achieving a CR or PR according to the 2014 Lugano Classification (Appendix 3) as assessed by Investigator and blinded IRC at the following time points: Cycle 3, Cycle 6, Cycle 12, Cycle 18, and Cycle 24. Subjects with a best response of unknown/non-evaluable response will be treated as non-responders, (i.e., they will be

Name of Investigational Product: Tazemetostat (EPZ-6438)

Name of Active Ingredient: Tazemetostat

included in the denominator when calculating the percentage). ORR will be presented with corresponding 2-sided 95% CIs. This analysis will be performed on a subset of the FAS that includes all subjects with WT EZH2 status.

Secondary Efficacy Endpoints:

- **PFS:** The PFS, defined as the time from the first dose of study drug to the earliest date of disease progression per the 2014 Lugano Classification (Appendix 3) or death from any cause, whichever occurs first, will be assessed by IRC. PFS will be estimated using Kaplan-Meier method and presented with corresponding 2-sided 95% CIs. PFS will be analyzed using the FAS.

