14.6. Determination of Sample Size and Criteria for Early Stopping Due to Futility

The primary objective of this study is to evaluate the ORR obtained in subjects with R/R FL and WT EZH2 status, treated with the combination of rituximab and tazemetostat. Given the historical data with single agent rituximab (McLaughlin, 1998; Leonard, 2019), the Sponsor would consider the combined regimen to be of no further interest if the ORR were 50% or less, but of considerable interest if the ORR were at least 70%.

Simon's two-stage design (Simon, 1989) will be used. The null hypothesis that the true response rate is 50% will be tested against the one-sided alternative. In the first stage, 15 subjects will be accrued. If there are 8 or fewer responses in these 15 subjects, the regimen will be considered as futile.

Subject enrollment will continue during futility analysis. If 9 responses or greater (CR + PR) are seen in the initial 15 subjects, additional subjects will be accrued for a total of 54 evaluable subjects. The Sponsor expects 80% of enrolled subjects to have WT EZH2 status. Consequently, the study will enroll approximately 43 WT subjects as well as approximately 11 MT subjects. With an estimated early dropout rate of 10%, this study estimates a total accrual of 59 subjects.

For the primary analysis, the null hypothesis will be rejected if 27 or more responses (CR + PR) are observed in the first 43 evaluable subjects regardless of mutation status. This design yields a one-sided type I error rate of 0.05 and power of 0.801 when the true response rate is 70%.

If the primary analysis is successful, full analysis will be conducted once 54 evaluable subjects are available regardless of mutation status. Subjects in the FAS will be stratified to 2 subgroups depending on their EZH2 mutation status (WT vs MT).

With an estimated 54 eligible subjects in the combined FAS, rates of individual AEs can be estimated to within at most \pm 14% (95% confidence interval). Any AE with a true rate of at least 5% is likely to be observed at least once (93% chance).

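### The plan gives no ORR interval matched to its decision rule: success is a one-sided 0.05 two-stage count in 43 subjects of any mutation status, while the planned interval is an unspecified two-sided 95% CI in the wild-type subset

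*Protocol*

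**What the plan says.** **The decision.** Protocol 14.6 sets the null at an ORR of 50% and the target at 70%. For stage 1: "If there are 8 or fewer responses in these 15 subjects, the regimen will be considered as futile". For the final look, the null is "rejected if 27 or more responses (CR + PR) are observed in the first 43 evaluable subjects regardless of mutation status". The stated operating characteristics are: "This design yields a one-sided type I error rate of 0.05 and power of 0.801 when the true response rate is 70" percent. The Protocol synopsis and SAP 3.2.1 repeat the rule.

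**The interval.** Protocol 14.2 states "ORR will be presented with corresponding 2-sided 95% confidence intervals (CIs"), and the synopsis says the same: "ORR will be presented with corresponding 2-sided 95% CIs". Neither names a method or mentions the two stages. The next sentence of 14.2 fixes the population: "This analysis will be performed on a subset of the FAS that includes all subjects with WT EZH2 status". Protocol 14.3 extends the analysis to the pooled FAS and to the mutant (MT) and rituximab-refractory subgroups. The Primary Analysis Set defined in Protocol 14, which is the first 43 evaluable subjects of any status, is given no interval.

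**The SAP.** Section 4.3 describes a one-sample chi-square test at one-sided 0.025, against the 0.05 kept in 3.2.1. Section 2 says the SAP supersedes the Protocol's statistical considerations. Sections 5.2, 8 and 9 say the study stopped early with 5 patients and that no futility or efficacy analysis will be done.

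**The concern.** A decision rule and the interval printed beside it should answer the same question, in the same subjects, at the same error level. Here three things differ.

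- **Level.** The lower limit of a two-sided 95% CI is a one-sided 0.025 bound, while the rule uses 0.05.
- **Sample space.** The rule holds its error at 0.05 only because of the stage 1 stop, and an ordinary interval ignores that stop.
- **Subjects.** The interval is for WT subjects in the FAS, while the decision uses the first 43 subjects of any status. The number 43 appears twice, which hides this: it is the size of the decision set and also the expected WT count (80% of 54 = 43.2). Of the 43 decision subjects, only about 34 would be WT (80% of 43 = 34.4).

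At stake is a marginal success. The trial could declare that 50% is ruled out while the interval a reader naturally looks to either contains 50% or describes other subjects.

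**Working it through.** **Inputs** (Protocol 14.6): n1 = 15, stop at 8 or fewer; n = 43, so n2 = 28; reject at 27 or more; p0 = 0.50, p1 = 0.70.

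**1. Reproduce the design.** The probability of passing stage 1 and ending on at least r responses is

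R(r; p) = Σ (x = 9 to 15) P(Bin(15, p) = x) × P(Bin(28, p) ≥ r − x).

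- R(27; 0.5) = 0.0499, against the stated 0.05.
- R(27; 0.7) = 0.804, against the stated 0.801, a difference of 0.003.

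Without the stage 1 stop, P(Bin(43, 0.5) ≥ 27) = 0.063. The stop is what brings the error below 0.05.

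**2. Ordinary intervals for x/43.** The Protocol names no method, so five were tried. For example, Wald at 27/43 has estimate 0.628 and standard error √(0.628 × 0.372 / 43) = 0.0737, so the lower limit is 0.628 − 1.96 × 0.0737 = 0.483. Clopper-Pearson solves P(Bin(43, p) ≥ 27) = 0.025 for its lower limit.

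| Lower limit | 95%, 27/43 | 95%, 28/43 | 90%, 27/43 |
|---|---|---|---|
| Clopper-Pearson | 46.7% | 49.1% | 49.1% |
| Wilson | 47.9% | 50.2% | 50.2% |
| Wald | 48.3% | 50.9% | 50.7% |
| Agresti-Coull | 47.8% | 50.1% | 50.2% |
| Jeffreys | 47.9% | 50.3% | 50.3% |

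At 27/43 every 95% interval contains 50%. At 28/43 only Clopper-Pearson does (49.1% to 79.0%). At 29/43 Clopper-Pearson also excludes it (51.5% to 80.9%).

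**3. How often this would happen.** The share of successes that land on 27 is [R(27) − R(28)] / R(27). For 27 or 28 it is [R(27) − R(29)] / R(27).

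| True ORR | R(27) | R(28) | R(29) | 27 only | 27 or 28 |
|---|---|---|---|---|---|
| 70% | 0.8044 | 0.7497 | 0.6694 | 6.8% | 17% |
| 65% | 0.5937 | 0.5065 | 0.4046 | 14.7% | 32% |
| 60% | 0.3491 | 0.2640 | 0.1838 | 24.4% | 47% |

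The last column applies only if Clopper-Pearson is assumed.

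**4. A matched bound.** Solving R(x; p) = 0.05 for p gives a one-sided 95% lower bound on the two-stage sample space: 50.01% at 27 (two-stage p = 0.0499) and 52.1% at 28 (p = 0.0279). Both exclude 50%, as the rule does.

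**5. The SAP 4.3 level.** The chi-square statistic is z = (x/43 − 0.5) / √(0.25/43). At 27, z = 1.68 and one-sided p = 0.0467, which does not reject at 0.025. At 28, z = 1.98 and p = 0.0237, which does. On the exact two-stage calculation, 28 gives 0.0279 and 29 gives 0.0141, so one-sided 0.025 would need 29. SAP 3.2.1 and SAP 4.3 therefore disagree on whether 27/43 is a success.

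**The case against.** Several objections have force.

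- **The interval is descriptive.** Success is fixed in advance by a response count, and the CI is only to be presented. A 95% CI beside a one-sided rule is common practice. This stands: the decision itself is not ambiguous under 14.6, and the gap is in what is reported with it.
- **Exactness is not in the text.** A reader might infer that the trial's own exact interval would contain 50% at both 27 and 28 responses. The documents do not support this. They never call the ORR interval exact, and they attach it to WT subjects in the FAS, not to the 43-subject decision set. The result at 27 does not depend on the method, but the result at 28 does.
- **Changing the level may be enough.** At 27/43, four of the five ordinary 90% intervals already exclude 50%. Only Clopper-Pearson does not. A two-stage interval is therefore not the only way to remove the conflict, but it agrees with the rule by construction and does not depend on the choice of approximation.
- **The error bars are not invalid.** A reader might conclude that ignoring the two stages spoils coverage. It does not. Applying ordinary 95% Clopper-Pearson to 15 or 43 subjects, according to where the trial stops, gives overall coverage of about 97% to 99% for true rates from 40% to 75%.
- **SAP 4.3 uses 0.025, which a 95% CI does match.** True, but the SAP also keeps 0.05 with the 27/43 rule, so this adds a second conflict and does not remove the first.
- **Nothing will be reported.** This stands in full.

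**Conclusion.** The point holds as a mismatch in level, method and population between the decision rule and the only ORR interval planned. It is not a finding of invalid inference.

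The main gap is that no interval or two-stage p-value is specified for the 43 subjects who determine success. If an ordinary 95% CI were used to fill that gap, it would contain 50% at 27/43. That is 6.8% to 24.4% of successes for true ORRs from 70% down to 60%. The larger range of 17% to 47%, which adds outcome 28, depends on assuming Clopper-Pearson.

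These figures assume the rule is applied exactly as written, with the stage 1 stop enforced, independent responses and a common response rate. The difference in population is arguably the larger defect, since no choice of method makes a WT interval describe a decision taken in all-comers. Because the study stopped with 5 treated patients, the practical effect on reported results is nil.

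**What to change.** In Protocol 14.2 and the SAP:

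1. For the 43-subject Primary Analysis Set, report the two-stage p-value, a two-sided 90% CI computed on the two-stage sample space (for example Koyama-Chen or Jung-Kim, with the lower limit equal to the one-sided 95% bound), and the design-adjusted (UMVUE) ORR.
2. Keep the ordinary 95% CI as a labelled supplement and for the WT, MT and rituximab-refractory summaries, and name its method.
3. State which analysis set each interval describes.
4. Reconcile the one-sided 0.025 in SAP 4.3 with the 0.05 in SAP 3.2.1. If 0.025 is meant, the 27/43 threshold and the stated power no longer apply.

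The cost is a few sentences, a short program and a second interval to explain. No patients are needed. With no efficacy analysis planned after termination, the change matters for the accuracy of the plan and for any reuse of its text.

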14.3. Secondary Efficacy Analyses

PFS is defined as the time from the first dose of study drug to the earliest date of documented disease progression per the 2014 Lugano Classification (Appendix 3) or death from any cause, whichever occurs first. Disease progression will be assessed by a blinded IRC. Cases without a reported PFS event will be censored at the time of the last tumor assessment. Median PFS, first and third quartiles will be estimated using Kaplan-Meier method on the FAS, if there are a sufficient number of PFS events (ie, relapses, progressions or deaths), and 2-sided 95% CIs will be estimated. Figures and listings of PFS will also be provided.

For each subject with a CR or PR, DOR is defined as time from the earliest date of CR or PR per the 2014 Lugano Classification (Appendix 3) to documented disease progression or death, whichever occurs first. DOR will be assessed by a blinded IRC If there are a sufficient number of responders who subsequently progress or die due to any cause. The median DOR, first and third quartiles, will be calculated from the Kaplan-Meier estimates using the FAS. The associated 2-sided 95% CIs will be estimated. A listing of DOR will be provided.

Analysis of ORR as a secondary endpoint will be similar to analysis of the primary efficacy endpoint but performed on FAS regardless of mutation status and the defined subgroups (MT EZH2 or rituximab refractory subjects).

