Assuming accrual takes place over 24 months, with at least an additional 12 months of follow-up for progression, there would be approximately 65% power to rule out a benchmark median PFS of 12 months against the alternative of a true PFS of 18 months (one-sided, 0.05 level test) in the primary analysis subset of 43 subjects with at least 26 PFS events. If PFS is similar in both subsets regardless of EZH2 status, then there would be 80% power for the same analysis in the combined FAS of 54 subjects with at least 33 PFS events.

The reporting of response rate in the MT EZH2 subset (anticipated to be 11 subjects) will have very little precision and is exploratory only. Note, the subjects with MT EZH2 status will be included in all primary safety analyses.

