3.2. Sample Size Considerations

3.2.1. Sample Size Justifications

The primary objective of this study is to evaluate the overall response rate obtained in subjects with R/R FL and wild-type (WT) EZH2 status, treated with the combination of rituximab and tazemetostat. Given the historical data with single agent rituximab ([McLaughlin, 1998](#) [Leonard, 2019](#)) we would consider the combined regimen to be of no further interest if the ORR were 50% or less, but of considerable interest if the ORR were at least 70%.

Simon's two-stage design (Simon, 1989) will be used. The null hypothesis that the true response rate is 50% will be tested against the one-sided alternative. In the first stage, 15 subjects will be accrued. If there are 8 or fewer responses in these 15 subjects, the regimen will be considered as futile.

Subject enrollment will continue during futility analysis. If 9 responses or greater (CR + PR) are seen in the initial 15 subjects, additional subjects will be accrued for a total of 54 evaluable subjects. The Sponsor expects 80% of enrolled subjects to have WT EZH2 status. Consequently, the study will enroll approximately 43 WT subjects as well as approximately 11 MT subjects. With an estimated early dropout rate of 10%, this study estimates a total accrual of 59 subjects. For the primary analysis, the null hypothesis will be rejected if 27 or more responses (CR + PR) are observed in the first 43 evaluable subjects regardless of mutation status. This design yields a one-sided type I error rate of 0.05 and power of 0.801 when the true response rate is 70%. If the primary analysis is successful, full analysis will be conducted once 54 evaluable subjects are available regardless of mutation status. Subjects in the FAS will be stratified to 2 subgroups depending on their EZH2 mutation status (WT vs MT). The sample size calculation is showing in [Appendix 1](#).

Assuming accrual takes place over 24 months, with at least an additional 12 months of follow-up for progression, there would be approximately 65% power to rule out a benchmark median PFS of 12 months against the alternative of a true PFS of 18 months (one-sided, 0.05 level test) in the primary analysis subset of 43 subjects with at least 26 PFS events. If PFS is similar in both subsets regardless of EZH2 status, then there would be 80% power for the same analysis in the combined FAS of 54 subjects with at least 33 PFS events.

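### The protocol states 65% and 80% power for a one-sided 0.05 test against a 12-month median PFS, but its analysis sections plan no such test

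*Protocol*

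**What the plan says.** Protocol 14.6 states that "there would be approximately 65% power to rule out a benchmark median PFS of 12 months" if the real median is 18, at a one-sided 0.05 level. That figure refers to the "primary analysis subset of 43 subjects with at least 26 PFS events". For the pooled group, SAP 3.2.1 repeats the protocol: "then there would be 80% power for the same analysis in the combined FAS of 54 subjects with at least 33 PFS events". The synopsis carries the same two figures.

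The analysis text is different in kind. Protocol 14.3 says: "Median PFS, first and third quartiles will be estimated using Kaplan-Meier method on the FAS, if there are a sufficient number of PFS events", followed by two-sided 95% confidence intervals. The synopsis methods say: "PFS will be estimated using Kaplan-Meier method and presented with corresponding 2-sided 95% CIs". Neither names a benchmark, a test statistic or a one-sided level. The secondary objective in 6.1.2 is also only to estimate median PFS. Section 14.3 censors event-free subjects at their last tumor assessment and analyses PFS on the FAS only, so no analysis there corresponds to the 43-subject figure.

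The SAP states that it supersedes the protocol's statistics. It adds no PFS test (its hypothesis section, 4.3, covers ORR only). Sections 5.2, 8 and 9 record early termination with 5 treated subjects and no efficacy analysis.

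**The concern.** A power statement has meaning only for a specified analysis. A benchmark, an alternative, a level, event counts and a power tell the reader that PFS will be tested against 12 months. The analysis section offers only a Kaplan-Meier median and interval. The obvious way to use that output against the benchmark is to ask whether the lower limit exceeds 12. That works at one-sided 0.025, not 0.05, and it uses little of the event information to which 14.6 ties its power. Had the trial run to plan, a regimen with the hoped-for 18-month median could have missed the benchmark more often than the stated power implies. The choice of test would also have been left open until after the data were seen.

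**Working it through.** **Inputs.** From 14.6: benchmark median 12 months, true median 18, one-sided 0.05, 26 events in 43 subjects, 33 events in 54, accrual over 24 months and at least 12 more months of follow-up. From the schedule in 7.1: scans at C3D1, C6D1, C12D1, C18D1 and C24D1 of 28-day cycles, about 1.8, 4.6, 10.1, 15.6 and 21.2 months. Assumed, because the documents do not say: exponential PFS and uniform accrual, so potential follow-up runs from 12 to 36 months.

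**1. The plan's own figures.** For a single-arm exponential test on the log median, power = Φ(√d × ln(18/12) − 1.645), with ln 1.5 = 0.4055.
- d = 26: 5.099 × 0.4055 = 2.067; minus 1.645 = 0.422; Φ = 66.4%.
- d = 33: 5.745 × 0.4055 = 2.329; minus 1.645 = 0.684; Φ = 75.3%.
- For 80%: d = ((1.645 + 0.842)/0.4055)² = 37.6, so about 38 events.

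Expected events agree with the plan's counts. With λ = ln 2/18 = 0.0385, P(event) = 1 − (e^(−12λ) − e^(−36λ))/(24λ) = 1 − (0.630 − 0.250)/0.924 = 0.589. That is 25.3 events in 43 subjects and 31.8 in 54, with power 65.4% and 73.9%. So 65% reproduces and 80% does not. A fixed-event one-sample log-rank approximation gives 80.4% at 33 events but 70.4% at 26. No method tried gives both stated figures.

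**2. The planned interval read as a decision.** The lower limit of the Kaplan-Meier median exceeds 12 exactly when the lower limit for S(12) exceeds 0.5. The true S(12) is 2^(−12/18) = 0.630. Simulated chance of success at a true median of 18, with the two-sided 95% interval (log-log to linear):

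| Dating of events and censoring | 43 subjects | 54 subjects |
|---|---|---|
| Exact event dates, censored at data cut | 33–46% | 45–56% |
| Exact event dates, censored at last scan | 31–40% | 36–45% |
| Progression dated at scheduled scans | 60–72% | 72–81% |

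An exact binomial count at one-sided 0.025 checks the low end of the first row: at least 29 of 43 has power 33.2%, and at least 35 of 54 has power 45.1%.

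In the third row, one-sided type I error at a true median of 12 is about 8–17%. Progression between scans is recorded late, so the pass rate rises under the null as well.

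**3. Where the shortfall comes from (exact dates).** There are two sources.
- Level: a one-sample log-rank or exponential test falls from about 66–67% and 75–76% at one-sided 0.05 to about 53–54% and 63–64% at 0.025.
- Efficiency: even a two-sided 90% interval, which matches one-sided 0.05, gives only about 45–59% and 56–68%. The interval rule uses what happens up to month 12, when 0.370 × 43 = 15.9 of 25.3 expected events, or 0.370 × 54 = 20.0 of 31.8, have occurred.

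**4. The natural replacement test.** A one-sample log-rank, z = (E − O)/√E against an exponential curve with median 12, has simulated power of about 67% and 76% with exact dates and type I error of about 4%. With progression dated at scans it shows about 82% and 90%, with type I error of about 12–15%. With exact event dates but censoring at the last scan, power falls to about 51% and 58%.

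**The case against.** The strongest reply is that 14.3 states no decision rule. The objective is estimation, Section 14 calls itself a summary, and the only PFS decision level in the documents is the one-sided 0.05 of 14.6. On that view a test is merely unspecified, and the percentages for the interval describe a rule supplied by the reader. This stands in part. A reader might infer that the plan itself delivers 33–46% and 45–56%. The documents do not support that, because the lower-limit rule is an inference. What remains is that the stated power has no planned analysis behind it.

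A reader might also argue that, with at least 12 months of follow-up, nobody is censored before month 12, so the decision is a simple count of subjects progression-free at 12 months. The documents contradict this. Section 14.3 censors at the last tumor assessment, and an event-free subject followed for 12 to 15.6 months was last scanned at about 10.1 months. In simulation about 9–10% of subjects are censored before month 12. The binomial count is a cross-check for the exact-date case only.

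It can further be said that scan dating brings the interval to 60–72% and 72–81%, ranges that contain 65% and 80%. That is true, but the type I error then exceeds the stated 0.05, so the promised test is still not delivered. The same sensitivity applies to any replacement figure for the log-rank test.

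Finally, the sample-size calculation in SAP Appendix 1 is redacted and may name the test behind 14.6. That would explain the figures. It would not put the test into the PFS analysis text.

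**Conclusion.** The concern holds as an inconsistency between the power statement and the analysis text. Protocol 14.6, the synopsis and SAP 3.2.1 power a one-sided 0.05 test; 14.3 and the synopsis methods plan only a Kaplan-Meier median with a two-sided 95% interval, on the FAS.

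Read through the inferred lower-limit rule, the planned output falls short of 65% and 80% with exact event dates under either censoring convention. It approaches them with scan-dated progression only by exceeding the stated error rate. All these figures rest on exponential PFS and uniform accrual. Separately, 80% is overstated for 33 events: about 75% on the exponential test, so part of the apparent 54-subject gap is that error.

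No stronger reading about the trial's outcome is available. With 5 treated subjects and no efficacy analysis, no reported PFS conclusion is affected.

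**What to change.** Choose one of two.

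1. Name in 14.3, the synopsis methods and the SAP the one-sided 0.05 test that 14.6 powers, for example a one-sample log-rank against an exponential curve with a 12-month median. Keep the Kaplan-Meier median and interval as description. Add the 43-subject analysis to 14.3 and say which subjects it contains. State the power as about 66–67% and 75–76%, conditional on exact progression dates. Check type I error and power by simulation under the actual scan schedule and the last-assessment censoring rule.

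2. Label PFS as descriptive, and remove the power statement from 14.6, the synopsis and SAP 3.2.1 or restate it for the Kaplan-Meier interval with its decision rule and assumptions.

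The cost is wording, plus one line of analysis code and a short simulation under the first option. No subjects, scans or visits are added. The drawbacks of the first option are reliance on an exponential reference curve, sensitivity to scan timing and a less favourable stated power. Because the trial has ended, the change corrects the design record only.
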